#### 5.3.3.2. Sensitivity and Supplementary Estimand for Primary Endpoint

To examine the robustness of the primary estimator under the different assumption from the main estimator. Sensitivity estimators will be conducted for primary estimand

**Sensitivity Estimator 1:**

- **Assumption:** Consider different analysis population
- **Sensitivity Estimator** Per-protocol analysis: participants with major deviations/identified by SRP (study responsible physician) will be excluded.

**Sensitivity Estimator 2:**

- **Assumption:** Consider different statistical model ANCOVA
- **Sensitivity Estimator** An ANCOVA model will be applied with the change from baseline in the CDAI at Week 12 as the response variable, treatment and population status (Bio-IR and Bio-NF) as fixed factors, and baseline CDAI score as a covariate.

**Sensitivity Estimator 3:**

- **Assumption:** Consider background concomitant medication steroids tapering as treatment failure
- **Sensitivity Estimator:** Imputing CDAI score based on last value carried forward (LVCF) method for participants who have any steroids tapering prior to week 8.

Other exploratory estimators may be conducted as necessary including but are not limited to

- Completer analysis for participant who completed week 12 treatment
- Imputing the CDAI score using the values prior to the treatment failure (ICE category 1-3) or prior to COVID-19 related ICE categories 4 and 5,
- Observed CDAI without incorporating treatment failure

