Concomitant corticosteroids must remain stable through Week 8. Participants receiving corticosteroids at baseline must begin tapering corticosteroids at Week 8. When corticosteroid tapering is commenced, the daily dose of prednisone or the equivalent should be decreased by 5 mg/week until the daily dose is 20 mg, and then by 2.5 mg/week until the daily dose is 0 mg. Participants receiving budesonide must begin tapering starting at Week 8. When budesonide tapering is commenced, the daily dose of budesonide should be decreased by 3 mg every 3 weeks until the daily dose is 0 mg. For participants who experience a worsening of disease activity while tapering oral corticosteroid or budesonide, further dose decreases may be suspended and/or their dose increased if deemed necessary by the investigator. The oral corticosteroid or budesonide dose, however, may not be increased above the baseline dose unless due to medical necessity. These participants will not be considered treatment failures unless their dose of oral corticosteroids or budesonide is increased above the baseline dose.

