### **Treatment Failure Rules:**

Treatment failure rules will be applied for all efficacy endpoints unless otherwise specified. In such a case, baseline values (at Week 0) will be assigned from the point of treatment failure onward, regardless of the observed data, for continuous endpoints, and participants will be considered as not achieving the respective endpoints for dichotomous endpoints. Treatment failure rules override other data handling rules.

For dichotomous endpoints, participants who have a treatment failure are considered as not achieving the respective endpoints after treatment failure. For continuous endpoints, participants who have a treatment failure will have their baseline values carried forward after treatment failure onwards.

The treatment failure rules will be applied to determine the final CDAI score. The treatment failure rules override the actual observation of the CDAI score. Participants who have any of the following events prior to the Week 12 visit will be considered a treatment failure and will be considered to have no change at Week 12 from their baseline CDAI score, regardless of the actual CDAI score:

- A Crohn's disease-related surgery (with the exception of drainage of an abscess or seton placement)
- Discontinuation of study intervention due to lack of efficacy or due to an adverse event (AE) of worsening Crohn's disease
- Specified changes in concomitant Crohn's disease medications described below.

The treatment failure rules for physician prescribed concomitant medication changes between Week 0 and Week 12 are:

1. Corticosteroids:
  - a. Initiation of oral corticosteroids (excluding budesonide) due to worsening Crohn's disease.
  - b. Initiation of oral corticosteroids (excluding budesonide) for more than 7 days due to reasons other than worsening Crohn's disease.
  - c. Initiation of oral budesonide due to worsening Crohn's disease.
  - d. Initiation of oral budesonide for more than 7 days due to reasons other than worsening Crohn's disease.
  - e. Increase by  $\geq 5$  mg above baseline in the prednisone equivalent dosage of oral corticosteroids (excluding budesonide) due to worsening Crohn's disease.
  - f. Increase by  $\geq 5$  mg above baseline in the oral prednisone equivalent dosage of oral corticosteroids (excluding budesonide) for more than 7 days due to reasons other than worsening Crohn's disease.

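### SAP Sensitivity Estimator 3 is labelled as counting steroid tapering as treatment failure, but its last-value-carried-forward imputation does not apply the SAP's own failure rule

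*SAP*

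**What the plan says.** SAP 5.3.3.2 gives Sensitivity Estimator 3 an assumption and a method. The assumption is: "Consider background concomitant medication steroids tapering as treatment failure". The method is: "Imputing CDAI score based on last value carried forward (LVCF) method for participants who have any steroids tapering", and the sentence ends by restricting this to tapering before Week 8.

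SAP 5.3.1 defines what a treatment failure means for a continuous endpoint: "baseline values (at Week 0) will be assigned from the point of treatment failure onward, regardless of the observed data, for continuous endpoints". For the primary endpoint, a participant who fails before Week 12 "will be considered to have no change at Week 12 from their baseline CDAI score, regardless of the actual CDAI score". SAP 5.3.2.1 and 5.3.3.1 apply the same baseline assignment to intercurrent event categories 1-3.

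Protocol 6.5.2 sets the taper timing: "Concomitant corticosteroids must remain stable through Week 8. Participants receiving corticosteroids at baseline must begin tapering corticosteroids at Week 8". Of participants who worsen while tapering, and whose taper is suspended or dose raised, it says: "These participants will not be considered treatment failures unless their dose of oral corticosteroids or budesonide is increased above the baseline dose".

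**The concern.** The label and the method give different answers for the same participant. The failure rule sets the change to zero. Last value carried forward (LVCF) keeps whatever change had been reached before the taper. A reader of the study report who sees tapering described as treatment failure will expect taperers to be scored as unimproved, and they are not. One programmer could follow the label and another the method line.

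The primary analysis depends on observed scores here. Tapering is neither a treatment failure event in SAP 5.3.1 nor a listed intercurrent event in 5.3.2.1, so CDAI recorded during a taper enters the primary MMRM as it stands. If a participant worsens on taper, LVCF replaces that worse score with a better earlier one. For that participant, an analysis labelled as a failure analysis is more lenient than the primary analysis it is meant to stress.

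**Working it through.** **1. The plan's own figure.** Inputs are a difference of 60 and SD 93 (SAP section 3), 54 and 36 participants (SAP 1.2), and 2-sided alpha 0.10 (SAP 5.3). SE = 93 × √(1/54 + 1/36) = 20.0. Power = Φ(60/20.0 − 1.645) ≈ 0.91, which agrees with the stated figure of about 90%.

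**2. Difference by visit.** SAP Attachment 2 gives assumed mean CDAI by visit, with a 50:50 mix of Bio-IR and Bio-NF. Baseline means are equal between arms, so a difference in score is also a difference in change (placebo − active).

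| Visit | Bio-IR | Bio-NF | Mean |
|---|---|---|---|
| Week 2 | 305 − 285 = 20 | 271 − 245 = 26 | 23 |
| Week 4 | 300 − 259 = 41 | 254 − 208 = 46 | 43.5 |
| Week 8 | 299 − 247 = 52 | 241 − 180 = 61 | 56.5 |
| Week 12 | 298 − 238 = 60 | 236 − 176 = 60 | 60 |

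I take the last value to be the last one before the taper starts. Among affected participants, LVCF then keeps a difference of 23 (from Week 2) or 43.5 (from Week 4) out of 60. The failure rule keeps 0. A taper before Week 8 would normally have Week 4 as its last preceding visit at the latest.

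**3. Effect on the overall estimate.** Let f be the share of participants with a qualifying taper. The documents do not give it, so it is assumed, equal in both arms and unrelated to outcome. Let d be the difference at the carried-forward visit.

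- Failure rule: 60(1 − f)
- LVCF: 60(1 − f) + f·d
- Gap: f·d

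| f | Failure rule | LVCF | Gap |
|---|---|---|---|
| 2% | 58.8 | 59.7 (Week 4) | 0.9 |
| 5% | 57.0 | 59.2 (Week 4) | 2.2 |
| 20% | 48.0 | 56.7 (Week 4) | 8.7 |
| 20% | 48.0 | 59.3 (Week 8) | 11.3 |

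The 2-5% rows illustrate the trigger as written, which reaches only participants who taper earlier than the protocol plans. The 20% rows illustrate a window extended to the mandated taper. Carrying from Week 2 under the present trigger gives a gap of 0.02 × 23 = 0.46 to 0.05 × 23 = 1.15.

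**4. If early tapering occurred in the active arm only.** The active mean change at Week 4 is the average of 259 − 323 = −64 and 208 − 302 = −94, that is −79. The gap is then f × 79, or 1.6 to 4.0 points at 2-5%.

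**5. Power.** The simulation used 4000 trials per scenario, the Attachment 2 means and covariances, and ANCOVA on baseline CDAI, population and treatment. It gave about 90% power with no tapering. At f = 5% in both arms, power was about 87% under the failure rule and 89% under LVCF from Week 4. At f = 20% it was about 78% against 87%, and 90% with LVCF from Week 8.

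**6. Against the primary analysis.** Take an active participant at the mean Week 4 change of −79 who starts tapering after that visit and is back at baseline by Week 12. The primary analysis scores 0 and the failure rule scores 0, while Estimator 3 scores −79.

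**The case against.** The best defence is that the failure rules apply except where the SAP specifies otherwise, and Estimator 3 names LVCF openly. This does not rescue the label. The same section lists imputing from values before the treatment failure as a separate exploratory option, so the SAP itself treats that as an alternative to its failure rule.

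The objection on size stands. Because the trigger is tapering before Week 8 and the protocol taper begins at Week 8, few participants should qualify, and either imputation would move the estimate little.

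Several stronger readings are tempting, and the documents do not support them:

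- *That the estimator tests the opposite assumption, or must look robust whatever the data.* LVCF assumes no further change after the last value. Since the assumed effect grows over time, carrying from Week 2 or Week 4 does lower the estimate. A taper before the Week 2 visit leaves the baseline value, exactly as the failure rule would.
- *That LVCF preserves a gain produced by steroids.* The background dose is meant to be stable through Week 8 in both arms, so nothing attributes the pre-taper change to steroids.
- *That this is the only check bearing on tapering.* SAP 5.3.4 and 5.7.8 give the primary comparison by baseline oral corticosteroid use, and participants not receiving steroids at baseline have nothing to taper.
- *That the trial's success decision is affected.* SAP 5.3.3.1 takes the decision intervals from the primary MMRM, and Attachment 1 calls the framework non-binding.

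**Conclusion.** The point holds as a mismatch between label and method. Run as written, Estimator 3 does not test whether the result survives counting taperers as failures, and it is more lenient than its name says. The primary analysis is untouched.

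The size depends on who qualifies. With the present trigger the two methods differ by about 0.9 to 2.2 points of 60, assuming 2-5% taper early, equally in both arms, with Week 4 carried forward. If the window is extended to the mandated taper, the gap is about 9 to 11 points at an assumed 20%. Correcting the window alone would therefore apply the mislabelled imputation to a much larger group, which is why the two should be settled together. The share on corticosteroids and the share tapering early are not in the documents. Tapering related to outcome would change these figures.

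**What to change.** Amend Sensitivity Estimator 3 before unblinding in one of two ways.

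- (a) Keep the failure assumption: assign baseline CDAI (change 0) from the qualifying taper onward, as in SAP 5.3.1. Label it a conservative, worst-case analysis, because protocol 6.5.2 does not count tapering itself as failure. With a wide window this dilutes the effect mechanically, and the label should make that plain.
- (b) Drop the failure label: call it a hypothetical estimator, set CDAI after the taper to missing, and analyse it in the same MMRM under missing at random.

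Under either option, reconcile the Week 8 trigger with the taper timing in protocol 6.5.2, and state whether Week 8 means the visit or the study day. This concerns the analysis text only and asks for no change to the taper.

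The cost is a few lines of SAP text and one extra run. The downside is a possibly less favourable sensitivity result.

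### Sensitivity Estimator 3 is labelled as a test of background steroid tapering, but its trigger stops at Week 8, when the protocol's mandated taper begins

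*SAP*

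**What the plan says.** SAP 5.3.3.2 gives the assumption behind Sensitivity Estimator 3 as "Consider background concomitant medication steroids tapering as treatment failure". The method is "Imputing CDAI score based on last value carried forward (LVCF) method", and it applies to "participants who have any steroids tapering prior to week 8".

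Protocol 6.5.2 sets the timing of background steroids. "Concomitant corticosteroids must remain stable through Week 8", and then "Participants receiving corticosteroids at baseline must begin tapering corticosteroids at Week 8". Budesonide follows the same timing: "Participants receiving budesonide must begin tapering starting at Week 8". The prednisone-equivalent dose "should be decreased by 5 mg/week until the daily dose is 20 mg, and then by 2.5 mg/week until the daily dose is 0 mg"; budesonide comes down by 3 mg every 3 weeks. The same section lets the investigator pause the taper or raise the dose if disease worsens. Such participants do not count as treatment failures unless the dose goes above its baseline level.

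For continuous endpoints, the treatment failure rules in SAP 5.3.1 mean that "baseline values (at Week 0) will be assigned from the point of treatment failure onward". The corticosteroid items in those rules cover initiations and increases, not reductions.

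**The concern.** The stated aim is general: background steroid tapering. Read against protocol 6.5.2, the trigger looks at the wrong side of Week 8. A participant who follows the protocol has no taper before the Week 8 visit and is mid-taper, or already off steroids, when the primary CDAI is measured at Week 12. The estimator leaves that participant's data unchanged.

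The question is a reasonable one to test. Steroid exposure between Weeks 8 and 12 may depend on response, because a taper can be suspended or partly reversed on worsening, and so it could come to differ between arms. As written, the only analysis named for this purpose would not address it.

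The label and the method also pull apart. Treatment failure elsewhere in the SAP means the baseline value, whereas this estimator carries the last value forward. Once the trigger is corrected, the choice between the two has a large effect on the result.

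**Working it through.** The documents state no figure for this analysis, so there is none to reproduce. The check has two parts.

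**1. Timing of the mandated taper**

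Inputs: the taper steps in protocol 6.5.2; the permitted baseline doses in protocol 5.1, criterion 9 (up to 25 mg/day prednisone-equivalent, or 9 mg/day budesonide). The first reduction is placed at Week 8.

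| Baseline dose | Dose after each step, from Week 8 | Steps before Week 8 | Steps from Week 8 to before Week 12 |
|---|---|---|---|
| 25 mg | 20, 17.5, 15, 12.5 | 0 | 4 |
| 20 mg | 17.5, 15, 12.5, 10 | 0 | 4 |
| 10 mg | 7.5, 5, 2.5, 0 | 0 | 4 |
| 5 mg | 2.5, 0 | 0 | 2 |
| Budesonide 9 mg | 6 (Week 8), 3 (Week 11) | 0 | 2 |

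No on-schedule step falls before Week 8, and several fall before the Week 12 CDAI.

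There is one qualification. SAP Table 1 puts Week 8 at Day 57, and footnote b of the protocol's Schedule of Activities allows ±4 days, so the visit can fall on Days 53 to 61. A mandated taper started at a visit on Days 53 to 56 would precede nominal Day 57. If week 8 means the calendar day rather than the visit, a few mandated tapers would be caught.

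**2. Size, using the SAP's planning means**

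Inputs from SAP Attachment 2, with the two populations weighted 50% each:

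- Week 8 difference (placebo minus active): Bio-IR 299 − 247 = 52; Bio-NF 241 − 180 = 61; average (52 + 61)/2 = 56.5.
- Week 12 difference: Bio-IR 298 − 238 = 60; Bio-NF 236 − 176 = 60; average 60.

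Let f be the share of participants on baseline steroids who taper on schedule. The documents do not give it. I take 20% and 40% as an assumed range (18 and 36 of 90), with 100% as the extreme, and assume f is equal across arms and populations and that steroid users follow the same mean profile as everyone else. CDAI is scheduled at Weeks 0, 2, 4, 8 and 12, so for an on-schedule taper the last value before the taper is Week 8 and only the Week 12 value is replaced.

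- Trigger as written, on-schedule tapers only: the difference stays at 60.
- Trigger extended, Week 8 value carried forward: 60(1 − f) + 56.5f = 60 − 3.5f.
- Trigger extended, baseline value assigned (change of 0 in both arms for those tapering): 60(1 − f).

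| f | As written | Last value before taper | Baseline value |
|---|---|---|---|
| 20% | 60 | 59.3 | 48 |
| 40% | 60 | 58.6 | 36 |
| 100% | 60 | 56.5 | 0 |

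**The case against.** The strongest defence is that the trigger is deliberate. A reduction before Week 8 departs from the protocol, the treatment failure rules do not list reductions, and Estimator 3 would then fill that gap. Capturing no compliant tapers would be the intended result. This reading is possible, but the assumption line does not limit itself to early or off-protocol tapers, and the per-protocol analysis (Sensitivity Estimator 1) may already remove some of those participants. The SAP should say which group is meant.

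A second defence is that the question is partly covered elsewhere. The subgroups in SAP 5.7.8 split on baseline oral corticosteroid use, and SAP 5.4.2 evaluates CDAI change at every post-baseline visit, Week 8 included. These help, but neither is a taper-specific analysis of the Week 12 endpoint.

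On the method, the treatment failure rules apply unless otherwise specified, and this estimator does specify otherwise. Last value carried forward is therefore permissible; what is loose is the label.

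A reader might also infer more than the documents support:

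- That the mandated taper confounds the treatment comparison. The taper rule is the same in both randomized arms at the same visit.
- That the estimator gives false reassurance. On the planning means, the carry-forward analysis moves the difference by only 0.7 to 1.4 points at the assumed shares.
- That compliant taperers should receive baseline values. Protocol 6.5.2 does not count even those who worsen during the taper as failures unless the dose exceeds baseline, and the baseline rule would shrink the difference to 48 or 36 simply because participants followed the protocol.

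**Conclusion.** The mismatch stands. Followed as written, Estimator 3 leaves on-schedule tapers between the Week 8 visit and Week 12 untouched. It would be too strong to say that it misses every mandated taper: that is exact only if week 8 means the visit, given the ±4-day window.

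The effect is modest and limited to one sensitivity analysis. The expected difference would move from 60 to about 59.3 or 58.6 CDAI points under the assumed 20% or 40% steroid use. Those figures rest on planning means that are not specific to steroid users, so they indicate scale and do not predict the result. The primary estimand, alpha, sample size and decision rules are unaffected. The point is worth correcting because, without it, the analysis does not test what its stated assumption says it tests.

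**What to change.** Reconcile SAP 5.3.3.2 with protocol 6.5.2; no dose or taper rule needs to change. In Sensitivity Estimator 3:

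- Apply the estimator to participants with any reduction in oral corticosteroid or budesonide dose before the Week 12 visit, including the taper that begins at Week 8.
- Carry forward the last CDAI before the taper.
- Drop the treatment-failure label, and do not assign baseline values to participants who taper as the protocol requires.
- If off-protocol tapers before Week 8 were the intended target, report them separately and say so.
- State whether week 8 means the visit or the calendar day.

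The cost is a short SAP edit and minor extra programming. Protocol 6.5 already requires concomitant therapies to be recorded with regimen and treatment period. The drawback is reliance on a Week 8 value standing in for Week 12, which is acceptable in a sensitivity analysis if stated. The edit should be made before unblinding.

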**5.3.3.3. Supplementary Estimand for Primary Endpoint****Estimand 2**

**Composite strategy:** This supplementary estimand will be same as Estimand 1 except for ICE categories 4 and 5, ICE categories 4 and 5 will be handled same as ICEs categories 1-3: baseline CDAI values will be used at all visits after an ICE.

**Analysis for Estimand 2:**

For testing of the primary endpoint using the supplementary estimand 3, the change from baseline in the CDAI score at Week 12 will be compared between experimental group and the placebo group using MMRM with categorical effects of population, treatment, time and treatment-by-time, and baseline CDAI score as a continuous covariate, with assumption of missing at random.

**Estimand 3**

**Hypothetical strategy:** This supplementary estimand will be handled by the hypothetical strategy for ICE categories 1-5: CDAI data at all visits after an ICE will be set to missing and assuming missing at random.

**Analysis for Estimand 3:**

For testing of the primary endpoint using the supplementary estimand 3, the change from baseline in the CDAI score at Week 12 will be compared between experimental group and the placebo group using MMRM with categorical effects of population, treatment, time and treatment-by-time, and baseline CDAI score as a continuous covariate, with assumption of missing at random.

#### Estimand 4

**Tipping point method:** This supplementary estimand will be used to assess the robustness of primary estimand using tipping point method to assess COVID-19 ICE impact as appropriate. For the change from baseline in CDAI, a delta adjustment multiple imputation method will be performed to evaluate the impact of missing data when deviating from the MAR assumption.

This method will employ the following 3 steps:

##### Step 1 - Multiple Imputation (MI)

Preparing monotone missing data pattern, and then run MAR-based multiple imputation with the regression option to impute missing values. For subjects with a non-monotone missing data pattern, ie, subjects may have ‘intermediate missing’ data between non-missing observations, imputing the intermediate missing values using the MCMC (Markov Chain Monte Carlo) method. This will be done using SAS PROC MI.

